Parents will engage in a 15-minute task with their child to measure baseline levels of child utterances and baseline fidelity of PRT techniques. This task is called the Structured Laboratory Observation (SLO) and will be modeled from Hardan et al. (2014). During the first five minutes, parents will be instructed to sit quietly and watch their child play (i.e., do not initiate interactions; however, parents can respond if child initiates). This period allows the child to become acquainted with the room and materials. Then, parents will be instructed to elicit language from the child for 10 minutes, using whatever strategies they want. Immediately following the SLO, parents will be asked to provide self-reported perceptions of positive and negative mood and stress levels during the parent and child interaction. In addition to measuring baseline child utterances with a caregiver, all children will engage in a 10-minute SLO with a trained PRT clinician to control for baseline levels of fidelity of PRT techniques. Finally, parents will complete paperwork to determine demographic information, child language and social behaviors, as well as levels of parenting stress, parent feelings toward child, and mindfulness.

Data will be collected over the course of four time points (pre-treatment, mid-treatment, post-treatment, 3-month follow-up) and weekly. See Table 1 for the complete battery at each timepoint. All questionnaire data will be collected either via paper and pencil or sent from and stored electronically through an online system called Research Electronic Data Capture (REDCap; Harris, Taylor, Thielke, Payne, Gonzalez, & Conde, 2009), hosted at Virginia Tech. REDCap is a secure, web-based application designed to support data collection for research studies. Weekly measures include a 10-minute home video of a participating parent interacting with his or her child while implementing PRT strategies and eliciting language. These videos will

be used in treatment to review strengths, areas of growth, and barriers encountered in the naturalistic settings as well as in research to monitor changes in child utterances and percentage of fidelity of implementing PRT strategies. In an effort to decrease demands from parents, we will provide families with Android tablets and instructions on how to upload the videos.

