Randomization. Eligible families will be randomly assigned to either the mindfulness enhanced mPRT or to pPRT as the control condition. The Randomization Module in REDCap will be completed by a research assistant, blind to the clinician completing the pre-treatment assessment. Groups will be matched on gender of caregiver to control for gender differences previously reported in parenting stress literature (Davis and Carter, 2008). Both caregivers are permitted to attend groups; however, one caregiver must identify as the primary reporter (i.e., individual who completes all self- and parent-report questionnaires, attends sessions regularly, and participates in all home videos).

If challenges with recruitment emerge, randomization rules may be adjusted. In this instance, once the period of recruitment has commenced and 3 or more families have completed the pre-assessment condition, a random number generator will be used to determine the group for the individuals.

Treatment (Appendix A). All families will receive the same dose of PRT parent training delivered in a previously studied package (e.g., Hardan et al., 2014) that includes 16 hours of group sessions and 4 hours of individual sessions, delivered over a 12-week timeframe. The format for teaching PRT techniques and abilities will be replicated from Hardan et al. (2014), who adapted the material from the manual, “How to Teach Pivotal Behaviors to Children with Autism” (Koegel et al., 1989) and has been previously implemented in a feasibility study by the current researchers.

Additionally, all parents will receive 6 hours total of group supplemental treatment that specifically targeted parenting stress either by mindfulness-based techniques or by psychoeducation (depending on random assignment). Materials from the psychoeducation group include didactic training on a variety of topics focusing on the parent, child and family outcomes. For example, literature on general parenting stress as well as parenting stress in parents of children with ASD was one topic presented in an informational manner, without providing instruction regarding specific skills training.

The mindfulness-enhanced treatment, on the other hand, provides specific skills as well as didactic information about applying mindfulness to the parenting role. Components from ACT as well as Mindful Parenting will be incorporated into the weekly sessions in a manner that applied the mindfulness skills to the newly learned PRT skills.

Measures

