Therapist fidelity of treatment implementation (Appendix B). A licensed clinical psychologist trained in PRT will view 5-6 group sessions out of the 11 total group sessions (i.e., 45 to 54% of the total group sessions) to assess for therapist fidelity of treatment implementation. The videos will be randomly assigned for viewing before all groups commenced and the

randomization was blind to treatment providers. Fidelity will be assessed on completion of specific session goals, therapeutic relationship, and level of group engagement.

Child utterances (Appendix C). The level or amount of child utterances during in-laboratory semi-structured tasks and in-home naturalistic environments will be coded by trained undergraduate research assistants using *Noldus The Observer XT* (version 12.0 software, Noldus Information Technology, Leesburg, VA, USA). All videos will be double coded by undergraduate research assistants who were blinded to treatment condition and treatment phase. Three total coders will complete double coding for all videos. Interrater reliability will be assessed by Kappa and Rho, due to the complexity of the coding system. All research assistants will attend group training in behavioral coding and child utterances and will attain above 80% fidelity with sample videos coded by a master's level clinician. As modeled in Hardan et al. (2014), child utterances consist of the following: unintelligible (e.g., sound produced by child that does not appear to demonstrate an attempt at a meaningful utterance; "lalalala"), imitative (e.g., parent models the word and encourages child to imitate exact word), verbally prompted (e.g., parent asks a question with open-ended response), nonverbally prompted (e.g., parent presents an opportunity for language by holding an object in sight and out of reach) and spontaneous (i.e., not prompted by the parent). To reduce variability, the amount of child utterances was expected to increase in both groups from pre SLO to post and follow-up SLO. Amount of child utterances were examined to determine effectiveness of treatment across groups.

In the current study, differences in child utterances will be calculated using changes in SLO and weekly videos will also be used to estimate changes in average utterances from weeks 1 and 2 to weeks 9 and 10. Because frequency/total counts were used for analyses, weekly videos will be excluded from analyses if they were less than 9 minutes in length.

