Group differences. Pending anticipated non-normal distributions of the small samples, Mann-Whitney U tests will be used to make baseline comparisons to compare independent samples (i.e., completers versus non-completers; mPRT versus pPRT). G*Power3 (Faul, Erdfelder, Lang, & Buchner, 2007) power analyses will be completed to evaluate the size of effect one can be expected to obtain given the obtained sample size, and $\alpha = .05$. A sample size of 95 will be necessary to detect a large effect ($r = .5$). Group comparisons will also be made at post-treatment to analyze differences in parent fidelity of PRT techniques and treatment satisfaction. To calculate effect size, the following formula will be ($r = Z/\sqrt{N}$). The

interpretation of r values are as follows: .5 = large effect, .3 = medium effect, .1 = small effect (Coolican, 2009; Fritz, Morris, & Richler, 2012).

In addition, to test within-group changes, non-parametric Wilcoxon Signed Rank Test (equivalent to a dependent t -test) will be used to compare baseline and endpoint/follow-up scores for each group across variables of interest. A sample size of 27 will be necessary to detect a large effect ($r = .5$) and 648 for a small effect ($r = .1$). Due to low power, effect sizes will also be calculated when determining change as a result of treatment.

Single-Subject Analyses. In addition to group change over time, individual level change will be calculated for parenting stress, parent mindfulness, and parent positive feelings toward child using Reliable Change Index (RCI; Jacobson & Truax, 1991). RCIs will be calculated to determine the magnitude of change needed to show meaningful change above and beyond standard error. RCI calculations will be completed by dividing the difference of scores between two timepoints (i.e., either pre-treatment and post-treatment or pre-treatment and follow-up), divided by the standard difference, which includes test-retest reliability and standard deviation of the original measure. RCI values above 1.96 are suggested to infer statistically significant and meaningful change. The test-retest reliabilities and standard deviations used to compute the S_{diff} score will be obtained from the literature. If test-retest reliability was not previously reported in literature, then Cronbach's alpha was used (from the literature).

Table 1
Assessment Schedule

Construct/ Measure	Pre-Tx	Mid	Weekly	Post-Tx	Follow-up
Sample Characterization					
ADOS-2	X				

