Appendix B
mPRT and pPRT Treatment Outline

Wk#	Session	PRT Training Focus	Mindfulness Training Focus	Psycho-education Focus	Worksheets for Homework
Pre	Screening/ Assessment (~2 hr)				
1	Group 1 (2 hr)	Introduction/Administrative; Overview of behavioral treatment approach and PRT (1 hr 15 min)	Overview of ACT components; Define current struggles/difficulties (30 min)	Overview of parent stress research (30 min)	"Play Interest Survey"
2	Group 2 (2 hr)	Detailed review of PRT motivational strategies (1 hr 15 min); Homework review (15 min)	Mindful awareness ("being present") - attention focused (30 min)	Understanding ASD and overlapping conditions (30 min)	"Setting goals for your child" + "Parent values"
	Individual 1 (1 hr)	Individual PRT goals; Demonstrate PRT through therapist-child interactions	Individual check-in on values (10 min)	Individual check-in on info (10 min)	N/A
3	Group 3 (2 hr)	Structured PRT learning opportunities; Natural/incidental learning opportunities	Discuss valued living, committed action and barriers (30 min)	Understanding ASD perspectives (30 min)	"Structured Teaching Brainstorm"
4	Group 4 (2 hr)	In-depth review*: Following the child's lead and shared control	Defusion exercises (30 min)	ASD Interventions I (30 min)	"Maintenance vs. Acquisition"
5	Group 5 (2 hr)	In-depth review*: Maintenance vs. acquisition tasks	Self-compassion (30 min)	ASD Interventions II (30 min)	N/A (plan to revisit child goals during individual session)
6	Midpoint Assessment (30 min) Combine with Individual session				
	Individual 2 (1 hr)	Demonstrate PRT through therapist coached parent-child interactions	Practicing self-compassion before/after session (10 min)	Individual check-in on info (10 min)	"Reinforcing attempts"
7	Group 6 (2 hr)	In-depth review*: Reinforcing reasonable attempts to respond	Incorporating mindfulness into daily life (30 min)	ASD Interventions III (30 min)	N/A
8	Group 7 (2 hr)	In-depth review*: Contingent vs. natural reinforcers	Introduce "self-as-context" or "observing self" (30 min)	ASD Resources: Local/National (30 min)	"Behavior Monitoring Form"
9	Group 8 (2 hr)	Tackling disruptive/problem behaviors	Practicing non-judgment and acceptance attitude (30 min)	Navigating service system (30 min)	N/A (plan to revisit child goals during individual session)

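### Within-arm gains in child utterances cannot show that PRT works, because both arms receive the same PRT and no arm is without it

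*Combined protocol and SAP*

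**What the plan says.** Child utterances are described under Measures, within the block headed as primary efficacy outcomes. There the plan states that "the amount of child utterances was expected to increase in both groups from pre SLO to post and follow-up SLO", and then: "Amount of child utterances were examined to determine effectiveness of treatment across groups". Changes are to be taken from the structured laboratory observation (SLO), with home videos compared between weeks 1-2 and weeks 9-10.

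On the arms, the Randomization paragraph says: "Eligible families will be randomly assigned to either the mindfulness enhanced mPRT or to pPRT as the control condition". The Treatment paragraph says: "All families will receive the same dose of PRT parent training". That training is "delivered over a 12-week timeframe". The arms differ in a 6-hour group supplement, mindfulness or psychoeducation. No waitlist, usual-care or other arm without PRT is described.

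On timing: "Data will be collected over the course of four time points (pre-treatment, mid-treatment, post-treatment, 3-month follow-up) and weekly".

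The SAP (Group differences) applies a Wilcoxon signed rank test within each group to baseline against endpoint or follow-up scores, and adds that "effect sizes will also be calculated when determining change as a result of treatment". The post-treatment comparisons between arms that it lists are parent fidelity and treatment satisfaction. Utterances are not among them.

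**The concern.** Taken together, these sections treat a rise from before to after treatment, seen in both arms, as evidence that treatment is effective. The children are young: the cognitive test and the behavior checklist are early-childhood instruments, and the ADOS-2 modules described are those for children with little or no language up to phrase speech. Such children may gain words over the study period with or without PRT, and they repeat the same laboratory task at four time points. With no arm free of PRT, these sources of change are credited to treatment.

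What is at stake is the conclusion on a primary outcome. Following the plan as written, the trial could report PRT as effective for language on evidence that would look much the same if PRT did nothing. The question that randomization can answer for utterances, whether the mindfulness supplement changes them relative to psychoeducation, has no named test.

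**Working it through.** **The plan's own figure.** For the within-group Wilcoxon test the SAP gives 27 for a large effect (.5) and 648 for a small one (.1). A noncentral-t calculation with Wilcoxon efficiency 3/π, one-sided alpha .05 and 80% power, with .5 and .1 entered as standardized mean changes, gives 28 and 649. That is close, though the document states neither sidedness nor power. The point below does not depend on these figures.

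**What each comparison can estimate.** Let P be the effect of PRT, S the effect of an arm's supplement, and G the background change from development and repeat testing.

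- Expected change in mPRT: P + S(m) + G
- Expected change in pPRT: P + S(p) + G
- Difference between arms: S(m) − S(p)

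A within-arm change estimates the sum, and P cannot be taken out of it without knowing G. The difference between arms removes G, which randomization balances on average, but removes P as well. No sample size alters this.

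**Interval.** Pre to post is 12 weeks, or 12 × 7 / 30.4 ≈ 2.8 months. Pre to follow-up is 2.8 + 3 ≈ 5.8 months.

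**Size, as an illustration.** Inputs:

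- 15 dyads in total (Participants), so 7 or 8 per arm.
- The test the SAP names: Wilcoxon signed rank within each arm, alpha .05, taken here as exact and two-sided.
- Assumed, because the documents give no figure: background growth of 0.2 to 0.5 SD, pre-post correlation ρ of 0.7 or 0.8, normally distributed changes, no dropout, and P = S = 0.

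The standardized change is dz = growth / √(2(1 − ρ)). For ρ = 0.7 the divisor is √0.6 = 0.775, so dz = 0.2/0.775 = 0.26 and 0.5/0.775 = 0.65. For ρ = 0.8 it is √0.4 = 0.632, so dz = 0.32 and 0.79.

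With no growth, the exact test rejects when the smaller rank sum is at most 2 (n = 7) or at most 3 (n = 8). Its true size is then 2 × 3/128 = 4.7% or 2 × 5/256 = 3.9%. Simulated rejection rates with growth only:

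| Correlation | Growth (SD) | dz | n = 7 | n = 8 |
|---|---|---|---|---|
| 0.7 | 0.2 | 0.26 | 8% | 8% |
| 0.7 | 0.5 | 0.65 | 28% | 30% |
| 0.8 | 0.2 | 0.32 | 10% | 10% |
| 0.8 | 0.5 | 0.79 | 39% | 42% |

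Every one of these rejections occurs with no treatment effect at all.

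**The case against.** The best defense is that the phrase about effectiveness across groups could mean a comparison between arms, which randomization would support. That reading is possible. It would still yield a conclusion about the supplement only, and the preceding sentence, which expects a rise in both groups, together with the within-arm tests in the SAP, makes the pre-post reading the natural one.

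The plan also has safeguards. Parents hold back for the first five minutes of the SLO so that the child gets used to the room, home videos measure utterances outside the laboratory, and coders are blinded to condition and phase. These limit novelty effects and coding bias. None of them controls for development. The clinician-led SLO addresses baseline fidelity and is not an untreated comparison.

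It is fair to add that this is a small study whose SAP acknowledges low power, and that at 7 or 8 per arm the inflation is modest at the lower end of the assumed range. That stands, and it is why the change asked for is one of wording and one added test, not a new arm.

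Three stronger readings are tempting and are not supported:

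- A reader might test all 15 dyads together and find much larger error rates. The SAP describes the test for each group separately and no pooled test.
- A reader might apply six months of growth throughout. Only the follow-up comparison spans that; post-treatment is at 12 weeks, and the home-video contrast covers about 8.
- A reader might infer that pPRT families take up more outside services, since five of the 11 psychoeducation titles in Appendix B concern interventions, resources or the service system, and that this hides a benefit of mPRT. Session titles do not show uptake. Any uptake they prompted would be a consequence of the assigned control condition, so it would not confound the comparison as randomized. Nor can it be said that services go unrecorded: no service-use measure is described, but the content of the Child History Form is not given, and Table 1 omits other measures that the text does schedule.

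**Conclusion.** The concern holds as a limit on what utterance gains can be made to mean. The core is a matter of design and rests on no assumed number: with the same PRT in both arms, neither the within-arm change nor the contrast between arms estimates the effect of PRT. The size is illustrative. Under the growth, correlation and distribution assumed above, a per-arm test would be significant with no treatment effect in about 8% to 42% of trials, against a nominal maximum of 5%. Skewed or tied counts, or dropout, would shift these figures.

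This does not invalidate the randomized comparison of mPRT with pPRT. It means that, for utterances, this comparison is the only one that supports a causal statement, and the SAP does not currently name it. The plan should be changed, at little cost.

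**What to change.** 1. **Measures, Child utterances.** Replace the sentence on determining effectiveness with: within-arm change in utterances is descriptive, is reported as change during PRT, and will not be reported as effectiveness of PRT.
2. **SAP, Group differences.** Make the same edit where the Wilcoxon paragraph describes change as resulting from treatment.
3. **SAP, Group differences.** Add a Mann-Whitney comparison of mPRT and pPRT on change in SLO utterances, from pre to post and from pre to follow-up, with the effect size r = Z/√N already defined there. State that this is the only randomized inference on utterances and that it concerns the supplement, not PRT.

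Optional: a brief item on outside services at each time point, reported descriptively by arm. This would help readers interpret the results but is not needed to correct the plan.

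The cost is two reworded sentences and one added test on data already being collected. With 15 dyads, against the 95 that the SAP itself gives for its group comparison, the added test will be imprecise, so its effect size should be read alongside the p-value. The real price is that the trial gives up an effectiveness claim for PRT that its design cannot support.

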Parent fidelity of PRT implementation (Appendix D). Parent fidelity of PRT

implementation will be coded by trained undergraduate research assistants using *Noldus The Observer XT* to measure changes in level of fidelity in-laboratory semi-structured tasks and in-home naturalistic environments over the course of treatment. All videos, including SLOs at all 4 timepoints as well as weekly videos (averaged for weeks 1-2 and weeks 9-10) will be coded by two research assistants separately (i.e., each research assistant coded all the videos separately). After videos were double-coded, the two research assistants will meet together to complete final consensus coding. All research assistants will attend group training in behavioral coding, behavioral management, and PRT techniques; they will attain at least 80% fidelity with two sample videos coded by PhD and master's level clinicians who were certified in PRT. Standardized measures of PRT fidelity (e.g., Bryson, Koegel, Koegel, Openden, Smith, & Neft, 2007; Minjarez et al., 2011) will be adapted for the current project to accommodate measurement every 30 seconds (as opposed to 1- or 2-minute intervals).

Fidelity of PRT implementation will include 5 total over-arching techniques (i.e., shared control, providing clear opportunities, interspersing maintenance trials, reinforcing attempts, and contingent/natural reinforcement of appropriate behavior), which could be further divided into 10 total components (i.e., following child's lead/child choice, natural reinforcer, attending to task, clear instructions, maintenance, task variation, natural, immediate, appropriate and attempts). The *Noldus* system will be automatically programmed to stop a video after every 30 seconds and prompt the research assistant to input fidelity information for all 10 components in a binary form (i.e., parent either achieved correct performance of component for the entire interval or did not, coded as 1 or 0 respectively). Total correct percentages will be calculated for each component and then averaged over the number of intervals to create a final correct percentage for total PRT

fidelity. Because final percentages will be individually calculated based on the total time they were coded, videos that range in length from 5 minutes to 10 minutes will be used for the current set of analyses.

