Parenting Stress Index, Fourth Edition (PSI-4; Abidin, 2012). The PSI-4 is the most widely used measure of parenting stress, not only in ASD but all parenting literature. The PSI-4 focuses on three domains of parenting stress: those relating to child characteristics, those attributed to parent characteristics as well as situational and life stressors. The PSI demonstrates strong internal consistency (alpha .96 or greater for each domain and test-retest reliability ranging from .65 to .96 for the Total Stress score). The PSI-4 child domain will be measured at four time points to measure change in parenting stress relating to child characteristics as a result of treatment.

Autism Parenting Stress Index (APSI; Silva & Schalock, 2012). The APSI consists of questions specific to parenting stress for parents of young children with ASD, such as behavioral symptoms and core deficits. Parents rate how much stress specific aspects of their child's health yield, ranging from "Not stressful" to "So stressful sometimes we feel we can't cope." The original validation of the measure was completed with a sample of children with ASD, other developmental disorders, and typical development. The APSI demonstrated good internal consistency ($\alpha = .83$) within the ASD population as well as high test-retest reliability ($r = .88$) for parents of children with ASD over a 4-month period of time.

Subjective Units of Parenting Stress Scale (Appendix E). An adaptation of the Subjective Units of Distress Scale, previously utilized in Singh et al., 2007, will be used to assess for levels of parenting stress immediately following all 10-minute SLOs.

Exploratory outcome variables.

Positive parent feelings toward child.

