Acceptance and Action Questionnaire-II (AAQ-II; Bond et al., 2011). The AAQ-II (Appendix I) is a seven-item measure designed to capture a person's level of experiential avoidance, where each item is ranked on 7 point scale ranging from "never true" to "always true". Higher scores on the measure reflect increased levels of experiential avoidance, the antithesis of psychological flexibility. The AAQ-II demonstrates good internal consistency (i.e., ranging from .78 to .87 across three samples) and acceptable test-retest reliability (i.e., .78 - .88). The AAQ-II will be administered at all time points.

Child problem behavior. The Child Behavior Checklist for Ages 1.5-5 (CBCL/1.5-5; Achenbach & Rescorla, 2001) is a parent report measure on child emotional and behavioral characteristics. Previous research suggests a bidirectional relationship between parent stress and child problem behaviors. Although the treatments in the current study focus on increasing child utterances and reducing parenting stress, changes in child problem behavior are also included to better understand baseline differences and change because of treatment. The CBCL demonstrates good internal consistency in general populations (.89 for internalizing and .92 for externalizing; Achenbach & Rescorla, 2001) as well as ASD specific populations (.80 for internalizing, .90 for externalizing; Pandolfi, Magyar, & Dill, 2009).

Statistical Analysis Plan

All data will be checked for normality, skewness, and kurtosis. In the case of small sample size and non-normal distributions, non-parametric analyses will be used to compare groups and changes over time.

Treatment feasibility and acceptability.

Parental adherence to treatment. Retention rate will be calculated by dividing the number of participants who were considered treatment completers by the total number of participants who were randomly assigned to a group. Because weekly videos were a crucial and core component of the PRT treatment package, the total number of videos submitted by parents will be calculated as a measure of adherence. Finally, parent weekly ratings of the amount of time spent implementing PRT skills in the home environment will be averaged to compare between groups.

Treatment satisfaction. The sections on perceived level of difficulty and helpfulness for PRT strategies will be averaged separately for each group.

Treatment efficacy and exploratory analyses.

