Child History Form	X				
Mullen	X				
Child Behavior Checklist	X				
Treatment Efficacy					
SLO Child Utterances	X	X	X	X	X
Treatment Satisfaction				X	
Therapist Fidelity of Treatment Implementation			X		
Parenting Stress					
PSI-4 (Child)	X	X		X	X
APSI	X	X		X	X
SUPSS	X	X		X	X
Positive Parent/Child Interactions					
PANAS	X	X		X	X
PFQ	X	X		X	X
Parent Mindfulness					
AAQ-II	X	X		X	X
FFMQ	X	X		X	X

Notes. PSI-4 = Parenting Stress Index Fourth Edition; APSI = Autism Parenting Stress Index; SUPSS = Subjective Units of Parenting Stress Scale (completed after 10 minute parent/child interaction); SLO = Structured Laboratory Observation; PANAS = The Positive and Negative Affect Schedule; PFQ = Parent Feelings Questionnaire; ADOS-2 = Autism Diagnostic Observation Schedule Second Edition; SRS-2 = Social Responsiveness Scale Second Edition; AAQ-II = Acceptance and Action Questionnaire; FFMQ = Five Facet Mindfulness Questionnaire

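### The text uses the CBCL to study change with treatment, but Table 1 schedules it only before treatment, so no change score would exist

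*Combined protocol and SAP*

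**What the plan says.** The Measures section describes the CBCL in its paragraph on child problem behavior, which falls under the heading "Exploratory outcome variables". It gives the instrument two jobs: "changes in child problem behavior are also included to better understand baseline differences and change because of treatment". It does not say when the CBCL is given.

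The Procedure section sets data collection at "four time points (pre-treatment, mid-treatment, post-treatment, 3-month follow-up) and weekly" and sends the reader to the schedule: "See Table 1 for the complete battery at each timepoint". In Table 1 the row "Child Behavior Checklist" stands in the Sample Characterization block with the ADOS-2, the Child History Form and the Mullen. It has one X, under Pre-Tx.

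The Statistical Analysis Plan, under Group differences, has two analyses that could take CBCL scores. At baseline, "Mann-Whitney U tests will be used to make baseline comparisons to compare independent samples". For change, the Wilcoxon signed rank test "will be used to compare baseline and endpoint/follow-up scores for each group across variables of interest". Those variables are not listed, and the SAP does not name the CBCL anywhere. The Reliable Change Index analysis covers parenting stress, mindfulness and positive feelings toward the child, but not child problem behavior.

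**The concern.** A change score needs at least two measurements on the same child. The text treats the CBCL as an outcome that may move with treatment; the schedule treats it as a one-time descriptor of the sample. Staff who work from Table 1 will collect one score per family, and a score not collected at its visit cannot be recovered afterwards.

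What would be lost is modest but real. The text includes the CBCL because parent stress and child problem behavior are thought to influence each other. Parenting stress is among the primary outcomes, including the PSI-4 child domain, and the treatment outline gives one group session (Group 8) to disruptive behavior. Without a later CBCL, the trial cannot describe on this measure whether child behavior moved alongside stress.

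**Working it through.** The plan gives no figure to reproduce here. The check compares text with schedule and counts the available scores.

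**Step 1. Marks in Table 1 at the four assessment visits.**

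| Measure | Pre-Tx | Mid | Post-Tx | Follow-up | Visits | Pre-to-later pairs |
|---|---|---|---|---|---|---|
| CBCL | X | | | | 1 | 0 |
| PSI-4 (Child), APSI, SUPSS, PANAS, PFQ, AAQ-II, FFMQ (each) | X | X | X | X | 4 | 3 |

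Where a measure has a Pre-Tx score, pairs = visits − 1: for the CBCL 1 − 1 = 0, for the others 4 − 1 = 3. The SAP's comparisons name only endpoint and follow-up against baseline, so 2 of those 3 pairs enter a named analysis. On that count the contrast is 0 against 2.

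**Step 2. Is this a fault in reading the table?** It does not look like one. The CBCL row has the same pattern as the ADOS-2, Child History Form and Mullen rows (one mark, then empty cells), while the repeated questionnaires keep all their marks. For the AAQ-II, text and table agree on all time points.

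**Step 3. Is a later CBCL scheduled elsewhere?** No. The CBCL paragraph gives no timing, and neither the Procedure section nor the treatment outline adds one.

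**Step 4. What can be analyzed under Table 1?**
- Baseline comparison of mPRT with pPRT (Mann-Whitney): possible, since one score per family is enough.
- Within-group change (Wilcoxon signed rank): not possible. Families with a CBCL pair: 0 of 15.

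**Step 5. What does each added visit give?** Post-Tx gives 1 pair per family (2 − 1); Post-Tx and Follow-up give 2 (3 − 1).

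**Step 6. How informative would a change result be?** Assume that the 15 families split 7 and 8 and that none drop out. The SAP states that 27 are needed to detect a large within-group effect. Then 7/27 = 0.26 and 8/27 = 0.30, so each group has 26% to 30% of that number. Any CBCL change result would be descriptive. This limit applies to every within-group test in the plan and does not bear on the mismatch itself.

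**The case against.** The best case on the other side is that baseline-only use was intended and half a sentence in the text is loose. Table 1 groups the CBCL with one-time measures, the Reliable Change Index list leaves out child problem behavior, and the SAP names no CBCL change analysis. On that reading one wording edit ends the matter, and adding visits goes beyond reconciliation.

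This reading is possible, but the documents do not establish it. The Measures section has its own part on eligibility and sample characterization, which describes only the ADOS-2 and the MSEL; the CBCL was placed with the exploratory outcomes instead. Nor is Table 1 reliable enough to settle the question. Its notes define the SRS-2, which has no row. Parent fidelity, a primary outcome coded from "All videos, including SLOs at all 4 timepoints as well as weekly videos", has no row either. The fidelity gap is the weaker example, because the SLO observations from which fidelity is coded are scheduled at all four visits, so no data would be lost. The table may have dropped the later CBCL marks, or the text may overstate the purpose.

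Two further points stand. The impact is small, being one exploratory outcome. And the document mixes future and past tense, so it is unclear whether post-treatment visits have begun; if they have, the data-collection remedy may be closed.

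**Conclusion.** The contradiction holds. If Table 1 is followed, the CBCL is collected at 1 of 4 assessment visits, 0 of 15 families have a change score, and the plan cannot report the treatment-related change in child problem behavior that its text says is included. The baseline purpose is unaffected.

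This should be corrected, but it does not threaten the trial. No primary analysis uses the CBCL, and it is not among the Reliable Change Index variables. The counts are conditional on staff following Table 1; the documents do not show which side is in error.

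**What to change.** Reconcile the child problem behavior paragraph with Table 1 before the first post-treatment visit, in one of two ways.

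1. **Keep the change purpose (preferred, because the text states it and lost scores cannot be recovered).** Mark the CBCL at Post-Tx in Table 1, the minimum for a change score, and at Follow-up if parent burden allows. In the SAP, name the scores to be used (for example internalizing and externalizing) in the Wilcoxon comparison with the r = Z/√N effect size, and label the analysis exploratory. Cost: one more parent questionnaire at one or two existing visits.
2. **Keep Table 1.** Delete the change purpose from the text, describe the CBCL as sample characterization for baseline comparisons only, and draw no conclusion about treatment-related change in child problem behavior. Cost: a wording edit with no effect on data collection, and the loss of the exploratory outcome.

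If the post-treatment and follow-up visits have already passed without a CBCL, only the second option remains.
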